Appendix 10. Physician's Global Assessment of CLE Disease Activity

A horizontal visual analog scale will be used to record the physician's assessment of the patient's CLE disease activity.

Instructions:

Place a mark on the line below to indicate the subject's current CLE disease activity (independent of the subject's self assessment):

Appendix 11. Subject's Global Assessment of CLE Disease Activity

A horizontal, visual analog scale will be used to provide the subject's overall assessment of CLE disease activity.

Instructions:

Place a mark on the line below to indicate how active your skin condition (CLE) has been over the last week:

I have no CLE

I have the worst CLE

## LIST OF ABBREVIATIONS

ACLE	acute cutaneous lupus erythematosus
AE	adverse event
ALT	alanine aminotransferase
AST	aspartate aminotransferase
BLQ	below the limit of quantitation
BMI	body mass index
CI	confidence interval
CLASI	cutaneous lupus erythematosus disease area and severity index
CLASI-A	CLASI-Activity
CLASI-D	CLASI-Damage
CLE	cutaneous lupus erythematosus
CRF	case report form
CSR	clinical study report
CTCAE	Common Terminology Criteria for Adverse Events
ECG	electrocardiogram
eCRF	electronic case report form
ET	early termination
FAS	Full Analysis Set
HLGT	high-level group term
HLT	high-level term
HLT	high-level term
LOQ	limit of quantitation
LTT	lower-level term
MedDRA	Medical Dictionary for Regulatory Activities
PK	pharmacokinetics
PT	preferred term
PTM	Placebo-to-match
Q1, Q3	first quartile, third quartile
QD	Once a day
SAE	Serious adverse events
SAP	statistical analysis plan
SCLE	subacute cutaneous lupus erythematosus
SD	standard deviation
SE	standard error
SGA	subject's global assessment
SLE	systemic lupus erythematosus
SLEDAI-2K	systemic lupus erythematosus disease activity index - 2000
SOC	system organ class

TEAE	treatment-emergent adverse event
TFLs	tables, figures, and listings
ULN	upper limit of normal
VAS	Visual Analog Scale
WHO	World Health Organization

## 1. INTRODUCTION

This statistical analysis plan (SAP) describes the statistical analysis methods and data presentations to be used in tables, figures, and listings (TFLs) in the clinical study report (CSR) for Study GS-US-497-5888. This SAP is based on the study protocol amendment 1 dated 01 July 2021 and the electronic case report forms (eCRF). The SAP will be finalized before database finalization. Any changes made after the finalization of the SAP will be documented in the CSR.

The decision to discontinue the study has been made on 18 October 2022. The screening has been stopped on 20 December 2021, with total 3 participants enrolled in the study. Of the 3 enrolled participants, 2 participants completed the study and 1 participant was prematurely terminated by sponsor.

This SAP describes the analyses to support the abbreviated CSR.

### 1.1. Study Objectives

The primary objective of this study is as follows:

- To evaluate the safety and tolerability of GS-5718 in participants with CLE with or without systemic lupus erythematosus (SLE)

The secondary objectives of this study are as follows:

- To characterize the PK of GS-5718 in participants with CLE with or without SLE

The exploratory objectives of this study are as follows:

[figure not shown]
## 1.2. Study Design

This is a Phase 1b, multicenter, randomized, sponsor-unblinded, placebo-controlled, 4-week study evaluating the safety and tolerability of GS-5718 in participants with CLE. Adult male or female participants at  $\geq 18$  and  $\leq 75$  years of age who either fulfill EULAR/ACR 2019 classification criteria for SLE or have biopsy-proven CLE and have acute CLE (ACLE)/subacute CLE (SCLE) with cutaneous lupus erythematosus disease area and severity index {Klein 2010} (CLASI) activity score of  $\geq 6$  during screening and Day 1 may be eligible for entry (refer to the protocol for complete inclusion and exclusion criteria). Eligible participants are randomly assigned to 1 of the following 2 treatment groups in a 2:1 ratio:

- GS-5718 115 mg once a day in addition to standard of care for 4 weeks (n = 8)
- Placebo-to-match (PTM) once a day in addition to standard of care for 4 weeks (n = 4)

A schematic of this study is provided in Figure 1-1.

**Figure 1-1. Study Design Schema**

## 1.3. Sample Size and Power

Sample size was determined based on practical considerations and no sample size calculation was performed. A sample size of 12 participants (8 participants randomized to GS-5718 and 4 participants randomized to placebo) would provide a suitable assessment of the descriptive safety and pharmacokinetics (PK) profile.

The enrollment was stopped after 3 participants were randomized.

## **2. TYPE OF PLANNED ANALYSIS**

### **2.1. Interim Analyses**

No interim analysis is planned.

### **2.2. Final Analysis**

The unblinded final analysis will be performed after all participants have completed the study, outstanding data queries have been resolved or adjudicated as unresolvable, and the data have been cleaned and finalized.

### **3. GENERAL CONSIDERATIONS FOR DATA ANALYSES**

Analysis results will be presented using descriptive statistics. For categorical variables, the number and percentage of participants in each category will be presented; for continuous variables, the number of participants (n), mean, standard deviation (SD) or standard error (SE), median, first quartile (Q1), third quartile (Q3), minimum, and maximum will be presented.

By-participant listings will be presented for all participants in the All Randomized Analysis Set and sorted by participant ID number, visit date, and time (if applicable). Data collected on log forms, such as AEs, will be presented in chronological order within the participant. The treatment group to which participants were randomized will be used in the listings. Age, sex at birth, race, and ethnicity will be included in the listings, as space permits.

#### **3.1. Analysis Sets**

Analysis sets define the participants to be included in an analysis. Analysis sets and their definitions are provided in this section. Participants included in each analysis set will be determined before the study blind is broken for analysis. The analysis set will be identified and included as a subtitle of each table, figure, and listing.

A listing of reasons for exclusion from analysis sets will be provided by participant.

##### **3.1.1. All Randomized Analysis Set**

All Randomized Analysis Set includes all participants who were randomized in the study.

##### **3.1.2. Full Analysis Set**

The Full Analysis Set (FAS) includes all randomized participants who took at least 1 dose of study drug. This is the primary analysis set for efficacy analyses.

##### **3.1.3. Safety Analysis Set**

The Safety Analysis Set includes all participants who took at least 1 dose of study drug. This is the primary analysis set for safety analyses.

#### **3.2. Participant Grouping**

For analyses based on the FAS, participants will be grouped according to the treatment to which they were randomized. For analyses based on the Safety Analysis Set, participants will be grouped according to the actual treatment received. The actual treatment received will differ from the randomized treatment only when their actual treatment differs from randomized treatment for the entire treatment duration.

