8.2. Analysis Conventions

8.2.1. Analysis Sets

8.2.1.1. All Randomized Analysis Set

The All Randomized Analysis Set includes all subjects randomized into the study. This is the primary analysis set for safety and efficacy listings.

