8.5. Safety Analysis

All safety data collected on or after the date when study drug was first dispensed up to the date of last dose of study drug plus 28 days will be summarized by treatment group (according to the study drug received). Data for the pretreatment and treatment-free follow up will be included in data listings.

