##### **4.2.1. Duration of Exposure to Study Drug**

Total duration of exposure to study drug will be defined as last dosing date minus first dosing date plus 1, regardless of any temporary interruptions in study drug administration, and will be expressed in weeks using up to 1 decimal place (e.g., 4.5 weeks). If the last study drug dosing date is missing, the latest date among the study drug end date, clinical visit date, laboratory sample collection date, and vital signs assessment date that occurred during the on-treatment period will be used for participants included in the final analyses. If month and year of the last dose are known, and the last study drug dosing date imputed above is different from the month collected, the last date of that month will be used. If only year of the last dose is known, and the last study drug dosing date imputed above is after the year collected, the last date of that year will be used; if the last study drug dosing date imputed above is before the year collected, the first date of that year will be used.

The total duration of exposure to study drug will be summarized using descriptive statistics and using the number (i.e., cumulative counts) and percentage of participants exposed through the following time periods: Baseline (Day 1), Week 1 (Day 8), Week 2 (Day 15) and Week 4 (Day 29). Summaries will be provided by treatment group for the Safety Analysis Set.

No formal statistical testing is planned.

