#### 7.1.6. Summaries of Adverse Events and Deaths

Treatment-emergent AEs will be summarized based on the Safety Analysis Set.

A brief, high-level summary of the number and percentage of participants who experienced at least 1 TEAE in the categories described below will be provided by treatment group. All deaths observed in the study will also be included in this summary.

The number and percentage of participants who experienced at least 1 TEAE will be provided and summarized by treatment group for the following:

- TEAEs
- TEAEs with Grade 3 or higher
- TEAEs with Grade 2 or higher
- TEAE Related to Study Drug
- TEAE Related to Study Drug with Grade 3 or Higher
- TEAE Related to Study Drug with Grade 2 or Higher
- TE Serious AE
- TE Serious AE Related to Study Drug
- TEAE leading to discontinuation of study drug
- TEAE leading to discontinuation of study
- TE AE leading to death (i.e., outcome of death)

Multiple events will be counted only once per participant in each summary.

In addition, data listings will be provided for all AEs and all SAEs indicating whether the event is treatment emergent, and all deaths.

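### Can the safety tables and the listings name different treatments for the same participant, and does the SAP need to change because of it?

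*SAP*

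**What the plan says.** Protocol 8.5 states that safety data "will be summarized by treatment group (according to the study drug received"). It does not say how to classify someone who received both products.

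SAP 3.2 follows the same principle: "For analyses based on the Safety Analysis Set, participants will be grouped according to the actual treatment received". It adds a working rule, under which actual treatment departs from randomized treatment "only when their actual treatment differs from randomized treatment for the entire treatment duration". The tables governed by this rule include exposure (SAP 4.2.1: "Summaries will be provided by treatment group for the Safety Analysis Set"), adverse events (SAP 7.1.6: "Treatment-emergent AEs will be summarized based on the Safety Analysis Set") and graded laboratory abnormalities (SAP 7.2.2.2).

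Listings have their own convention. SAP 3 presents them for the All Randomized Analysis Set and states: "The treatment group to which participants were randomized will be used in the listings". Protocol 8.2.1.1 names the same population ("This is the primary analysis set for safety and efficacy listings") and sets no treatment label. The listings include adverse events (SAP 7.1.6: "data listings will be provided for all AEs and all SAEs indicating whether the event is treatment emergent, and all deaths"), numeric laboratory results (7.2.1), vital signs (7.3) and ECG (7.5). The last three have no table of their measured values.

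**The concern.** Two things look wrong. First, if a participant took the other arm's product throughout, the exposure, adverse event and graded laboratory tables would show the drug received, while the listings would show the opposite arm. Second, if the product was wrong for only part of the course, the participant would sit in the randomized arm in both tables and listings, and neither SAP 3.2 nor SAP 7 requires a footnote.

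Safety is the primary objective, and the SAP supports an abbreviated report in which much of the safety data appears only in listings. For numeric laboratory values, vital signs and ECG, the listing label is the treatment label the reader sees. A wrong or silent label there could attribute a finding on GS-5718 to placebo, or the reverse.

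**Working it through.** There is no powered figure to reproduce: both documents say the sample size was set on practical grounds. The check is to apply the two conventions to each kind of dosing history and see what label results.

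**Inputs**
- Table rule: SAP 3.2. Listing rule: SAP 3.
- Course length: at most 4 weeks (Protocol 3.4), so 28 daily doses. It is 29 if dosing runs from Day 1 through Day 29, the Week 4 day in SAP 4.2.1.
- Daily dose: a 100 mg tablet plus a 15 mg tablet, 115 mg in total (Protocol 5.3).
- Dispensing: scheduled once, on Day 1 (Protocol Appendix 3).
- Randomized: 3 participants (SAP 1.3).

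**Case by case**

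| Dosing history | Safety tables | Listings | Do they agree? |
|---|---|---|---|
| As assigned | Randomized arm (= received) | Randomized arm | Yes |
| Wrong product on some days | Randomized arm | Randomized arm | Yes, without a required note |
| Wrong product on every day | Arm received | Randomized arm | No |
| Randomized, never dosed | Not in the Safety Analysis Set | Randomized arm | Not applicable |

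1. The labels diverge only in the third row. The fourth row shows why the listing convention is reasonable: a person who took no drug has no treatment received, so only the randomized label covers everyone listed.

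2. In the second row, the longest error that leaves a participant in the randomized arm is one day short of the full course: 27/28 = 96.4%, or 28/29 = 96.6%. These are limits of the rule, not observed exposures. With a single scheduled dispensing, a switch of product partway through is unlikely.

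3. A further case is one wrong tablet strength taken every day. The product contrary to assignment would make up 15/115 = 13.0% or 100/115 = 87.0% of the daily dose, and the exposure would match neither arm. This assumes that each strength has its own bottle and that one bottle can be misassigned alone. The documents state neither: Protocol 5.5 records a kit number and Protocol 5.1 runs assignment through the IRT. SAP 3.2 can be read either way here, because the product differs every day but only in part.

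4. Tracing an error: the SAP plans by-participant listings of the randomization scheme and of lot number and bottle ID (4.1), drug administration and accountability (4.2.2) and important deviations (4.3). Listings are sorted by participant ID, so a reader follows 3 people across them.

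5. Effect on results: neither document reports a dosing error. Both primary endpoints, adverse events and laboratory abnormalities, remain tabulated by treatment received under SAP 3.2. A note beside the data would move no event from one column to another. If a whole-course error were found, it would affect the listing label of 1/3 = 33.3% of participants and leave the tables as they are.

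**The case for a change.** The best case for a change is that listings carry more weight here than usual. The protocol planned group summaries of vital signs and ECG (8.5.4.1) and summaries of selected laboratory data (8.5.3), under a section that groups by drug received. The SAP moves these to listings, where the randomized label applies, and SAP 7.7 mentions fewer summaries but not the label. With 3 participants in two arms, the smaller arm holds at most one, so one mislabelled person could be a whole column. The tracing listings are not a guarantee either: the SAP does not define an important deviation, the bottle listing covers assigned drug, and medication errors reportable under Protocol 7.1.3 and 7.3.4 get no listing of their own.

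All of that is accurate. What stands is narrow: no text requires a note next to the safety data. It does not show that the SAP contradicts itself, since it sets two explicit conventions for two kinds of output on two populations. Nor does it show a departure from Protocol 8.5, which leaves mixed exposure open; SAP 3.2 supplies a rule for it.

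A more detailed rule could also do harm. Fixing any partial error in the randomized group would tabulate a placebo participant taking 100 of 115 mg daily as placebo. That fits poorly with grouping by drug received and with one reading of SAP 3.2. Such a case is better judged on its facts, if it ever arises.

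**Conclusion.** No change to the plan follows. Labelling listings by randomized arm and safety tables by treatment received is a workable pair of conventions, and the listing label fits the population listed. The gap is the lack of a required note for a participant whose actual product differed, wholly or in part, from the assigned one. An analyst who knew of such an error would add that note without being told, and SAP 1 already provides for recording later changes in the clinical study report.

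The effect is zero if dosing followed assignment. After a whole-course error in one participant, the listings for 1 of 3 people would carry a different arm from the tables, with no table count altered by adding a note. After a shorter error, tables and listings would agree.

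This rests on two points: the documents report no dosing error, and with so few participants the planned listings can be read side by side.

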### **3.3. Strata and Covariates**

This study does not use a stratified randomization schedule when enrolling participants. No covariates will be included in efficacy and safety analyses.

### **3.4. Examination of Participant Subgroups**

There are no prespecified participant subgroups for efficacy and safety analyses.

### **3.5. Multiple Comparisons**

Adjustments for multiplicity will not be made.

### **3.6. Missing Data and Outliers**

#### **3.6.1. Missing Data**

In general, missing data will not be imputed unless methods for handling missing data are specified. Exceptions are presented in this document.

For missing last dosing date of study drug, imputation rules are described in Section 4.2. The handling of missing or incomplete dates for AE onset is described in Section 7.1.5.2, and for prior and concomitant medications in Section 7.4.

#### **3.6.2. Outliers**

Outliers will be identified during the data management and data analysis process, but no sensitivity analyses will be conducted. All data will be included in the data analysis.

### **3.7. Data Handling Conventions and Transformations**

The following conventions will be used for the imputation of date of birth when it is partially missing or not collected:

- If only month and year of birth is collected, then “15” will be imputed as the day of birth.
- If only year of birth is collected, then “01 July” will be imputed as the day and month of birth.
- If year of birth is missing, then date of birth will not be imputed.

Partial CLE/SLE diagnosis dates will be imputed using same rules as for the partial dates of birth.

In general, age collected at Day 1 (in years) will be used for analyses and presented in listings. If age at Day 1 is not available for a participant, then age derived based on date of birth and the Day 1 visit date will be used instead. If an enrolled participant was not dosed with any study

drug, the randomization date will be used instead of the Day 1 visit date. For screen failures, the date the first informed consent was signed will be used for the age derivation. Age required for longitudinal and temporal calculations and analyses (e.g., estimates of creatinine clearance, age at date of AE) will be based on age derived from date of birth and the date of the measurement or event, unless otherwise specified.

The data that are continuous in nature but are less than the lower limit of quantitation (LOQ) or above the upper LOQ will be imputed as follows:

- A value that is 1 unit less than the lower LOQ at the same precision level of the originally reported value will be used to calculate descriptive statistics if the datum is reported in the form of “< x” (where x is considered the lower LOQ). For example, if the values are reported as < 50 and < 5.0, values of 49 and 4.9, respectively, will be used to calculate summary statistics. An exception to this rule is any value reported as < 1 or < 0.1, etc. For values reported as < 1 or < 0.1, a value of 0.9 or 0.09, respectively, will be used to calculate summary statistics.
- A value that is 1 unit above the upper LOQ will be used to calculate descriptive statistics if the datum is reported in the form of “> x” (where x is considered the upper LOQ). Values with decimal points will follow the same logic as above.
- The lower or upper LOQ will be used to calculate descriptive statistics if the datum is reported in the form of “≤ x” or “≥ x” (where x is considered the lower or upper LOQ, respectively).

### **3.8. Analysis Visit Windows**

#### **3.8.1. Definition of Study Day**

Study day will be calculated from the first dosing date of study drug and derived as follows:

- For postdose study days: Assessment Date – First Dosing Date + 1
- For days prior to the first dose: Assessment Date – First Dosing Date

Therefore, study day 1 is the day of first dose of study drug administration.

### **3.8.2. Definition of Baseline**

Baseline will be defined as the last nonmissing value on or prior to the first dosing date of study drug. All visits, including unscheduled visits, prior to the first dosing date of study drug, will be used for baseline derivation. If there are multiple records with the same time or no time recorded on the same day, the baseline value will be the average of the measurements for continuous data, or the measurement with the lowest severity (e.g., normal will be selected over abnormal for safety electrocardiogram [ECG] findings) for categorical data.

### **3.8.3. Analysis Visit Windows**

No analysis visit windows will be derived for this study. The baseline and relevant nominal visits as recorded on the CRF will be used when data are summarized by visit. Any data relating to unscheduled visits will not be assigned to a particular visit or time point. However, the following exceptions will be made:

- An unscheduled visit prior to the first dosing of study drug may be included in the calculation of the baseline value, if applicable.
- Unscheduled visits after the first dose of study drug will be included in determining the maximum postbaseline toxicity grade.
- For participants who prematurely discontinue from the study, early termination (ET) data will be summarized as a separate visit, labeled as “Early Termination Visit”.
- Data collected on a follow-up visit will be summarized as a separate visit and labeled “Follow-up Visit”.
- Data obtained after the follow-up visit or last dose date plus 28 days (whichever is later) will be excluded from the summaries but will be included in the listings.

All records will be listed by collection date.

## **4. PARTICIPANT DISPOSITION**

### **4.1. Participant Enrollment and Disposition**

Key study dates (i.e., first participant screened, first participant randomized, last participant randomized, last participant last visit for the primary endpoint, and last participant last visit for the clinical study report) will be provided.

No summary of participant enrollment will be provided. Relevant patient enrollment information will be presented in a by-participant listing.

The randomization schedule used for the study will be provided as an appendix to the CSR. Randomization scheme will be presented in a by-participant listing.

A summary of participant disposition will be provided by treatment group. This summary will present the number of participants in each of the categories listed below:

- Screened
- All Randomized Analysis Set
- Safety Analysis Set
- Full Analysis Set
- Completed study drug
- Did not complete study drug with reasons for premature discontinuation of study drug
- Completed study
- Did not complete the study with reasons for premature discontinuation of study

For the status of study drug and study completion, and reasons for premature discontinuation, the number and percentage of participants in each category will be provided. The denominator for the percentage calculation will be the total number of participants in the Safety Analysis Set corresponding to that column. In addition, a flowchart will be provided to depict the disposition.

The following by-participant listings will be provided by participant identification (ID) number in ascending order to support the above summary tables:

- Reasons for premature study drug or study discontinuation
- Reasons for exclusion from analysis sets
- Lot number and bottle ID of assigned study drugs

